## 9.3.1 Determination of Sample Size

Part B of this study is designed to determine the efficacy in PROS and PS patients treated with a daily dose of miransertib. The primary endpoint for Cohort 1 and Cohort 2 is response rate as assessed by blinded reviewers (with adjudication) using protocol response criteria. Sample size is justified based on the precision of a 95% confidence interval on the response rate. To exclude a clinically irrelevant response rate of 5%, the lower limit of the 95% confidence interval should be higher than 5%.

- Cohort 1, PROS: A sample size of n=20 participants will provide a two-sided exact Clopper-Pearson 95% confidence interval of (6%, 44%) on an observed response rate of 30%.
- Cohort 2, PS: A sample size of n=10 participants will provide a two-sided exact Clopper-Pearson 95% confidence interval of (7%, 65%) on an observed response rate of 30%.

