# 2.2 Overall Study Design

This is an open-label, multicenter Phase 1/2 study of oral miransertib administered daily to patients with PROS and PS. The study will be conducted at up to 20 sites globally.

Part B will enroll approximately 65 participants with clinical diagnosis of PROS or PS with documented somatic PIK3CA or AKT1 mutations. Part B will be comprised of 4 Cohorts: Cohort 1 will enroll 20 participants with PROS with a measurable lesion by the study-

standardized volumetric MRI. Cohort 2 will enroll 10 participants with PS with measurable CCTN and pre-CCTN lesional area by the study-standardized photography. Cohort 3 will enroll approximately 25 PROS or PS patients who do not meet the eligibility criteria for enrollment in Cohort 1 or Cohort 2. Cohort 4 will enroll participants previously treated with miransertib or currently receiving miransertib Compassionate Use/Expanded Access.

In Part B (except Cohort 4), participants will receive miransertib at the 15 mg/m^2 qd dose level during the first 3 cycles, (a cycle of therapy is considered to 28 days). The dose will be increased to 25 mg/m^2 qd provided no clinically significant drug-related toxicity is observed. Participants who experienced miransertib-related toxicity or are unable to tolerate study medication during the first 3 cycles may be treated at lower doses.

Participants enrolled in Cohort 4 will continue treatment at the dose they were on at the time of enrollment, but their dose should not exceed the 25 mg/m^2.

For all participants, actual dose will be calculated using BSA, per the DuBois formula.

Participants will stay on treatment for up to 48 cycles.

To better understand the natural history of the disease of each individual participant, all participants will be asked to provide a detailed history of their disease, including prenatal and postnatal evaluations, and surgical operations, results of any functional tests performed before the study enrollment, and, when possible, imaging scans (eg, CT, MRI, US), photographs, and/or video recordings collected before study enrollment.

PIK3CA or AKT1 somatic mutations must be documented before enrollment. If the status is unknown, an archival or fresh tissue biopsy must be collected and tested for PIK3CA or AKT1 somatic mutations. For all enrolled participants, archival or fresh tissue biopsy should be collected and sent to the Sponsor or designee.

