2.3 Sample size

Part A:

Enrollment in Part A was stopped upon approval of Protocol Amendment 6. 25 to 40 participants were planned to be enrolled.

Part B: Cohorts 1 and 2

Part B of this study was originally designed to determine the efficacy in PROS and PS patients treated with a daily dose of miransertib. The primary endpoint for Cohort 1 and Cohort 2 was response rate as assessed by blinded reviewers (with adjudication) using protocol response criteria. The sample size was justified based on the precision of a 95% confidence interval (CI) on the response rate. To exclude a clinically irrelevant response rate of 5%, the lower limit of the 95% CI should be higher than 5%.

- Cohort 1, PROS: A sample size of n=20 participants will provide a two-sided exact Clopper-Pearson 95% CI of (6%, 44%) on an observed response rate of 30%.
- Cohort 2, PS: A sample size of n=10 participants will provide a two-sided exact Clopper-Pearson 95% CI of (7%, 65%) on an observed response rate of 30%.

With Protocol Amendment 7, efficacy assessments will no longer be collected, and the primary objective of the study is the evaluation of safety and tolerability of miransertib.

Part B: Cohorts 3 and 4

Approximately 25 and 10 patients will be enrolled in Cohorts 3 and 4, respectively.

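### Cohort 1 sample size: the exact 95% interval (6%, 44%) printed for n=20 does not belong to the stated 30% response rate

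*Protocol*

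**What the plan says.** Protocol 9.3.1 (Determination of Sample Size) bases the sizes of Cohorts 1 and 2 on the precision of a 95% confidence interval for the response rate. To rule out a response rate of 5%, judged clinically irrelevant, it requires that "the lower limit of the 95% confidence interval should be higher than 5"%.

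For Cohort 1 it states that "n=20 participants will provide a two-sided exact Clopper-Pearson 95% confidence interval of (6%, 44%) on an observed response rate of 30"%. SAP 2.3 (Sample size) gives the same figures: "n=20 participants will provide a two-sided exact Clopper-Pearson 95% CI of (6%, 44%) on an observed response rate of 30"%.

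For Cohort 2 the protocol states that "n=10 participants will provide a two-sided exact Clopper-Pearson 95% confidence interval of (7%, 65%) on an observed response rate of 30"%, and the SAP again agrees.

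The Cohort 1 target is still in the current design text. Protocol 2.2 says "Cohort 1 will enroll 20 participants with PROS with a measurable lesion", and SAP section 2 gives the same number. SAP 2.3 presents the calculation as history and adds: "With Protocol Amendment 7, efficacy assessments will no longer be collected". Protocol 9.3.1 still describes the efficacy design in the present tense.

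**The concern.** The printed interval looks wrong before any calculation. For a rate below 50%, an exact binomial interval reaches further above the estimate than below it. The Cohort 2 interval does so: 23 points below 30% and 35 above. The Cohort 1 interval does the reverse: 24 points below 30% and only 14 above.

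This interval is the only numerical justification given for enrolling 20 participants in Cohort 1. As printed, a reader cannot tell whether the design rested on an observed rate of 20% or 30%, and anyone who describes the original design from either document will repeat a false statement of its precision. Protocol section 8 leaves open that responses already collected may be analysed, and a reader of such results would look here for the planned precision.

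**Working it through.** **Inputs** (Protocol 9.3.1, repeated in SAP 2.3): n = 20; two-sided exact Clopper-Pearson; 95% confidence, so 0.025 in each tail; observed rate 30%, so x = 0.30 × 20 = 6; lower limit required to exceed 5%.

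**Formula.** For x responders out of n:

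- lower limit = 0.025 quantile of Beta(x, n − x + 1)
- upper limit = 0.975 quantile of Beta(x + 1, n − x)

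**Step 1: check the method on Cohort 2.** For 3/10, the 0.025 quantile of Beta(3, 8) is 6.67% and the 0.975 quantile of Beta(4, 7) is 65.25%. This rounds to (7%, 65%), as printed. A Wald interval for 3/10 would be (1.6%, 58.4%). The method named in the plan is therefore the one used for Cohort 2.

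**Step 2: apply it to Cohort 1 as stated.** For 6/20, the 0.025 quantile of Beta(6, 15) is 11.89% and the 0.975 quantile of Beta(7, 14) is 54.28%. The interval is (12%, 54%), not (6%, 44%). Direct binomial tails confirm it: P(X ≥ 6) at 11.89% and P(X ≤ 6) at 54.28% are both 0.025. The differences from the printed limits are 11.89 − 6 = 5.89 points and 54.28 − 44 = 10.28 points, far beyond rounding.

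**Step 3: find what (6%, 44%) belongs to.** Exact 95% intervals at n = 20:

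| Responders | Rate | Lower | Upper | Width (points) | Lower limit above 5%? |
|---|---|---|---|---|---|
| 3/20 | 15% | 3.2% | 37.9% | 34.7 | no |
| 4/20 | 20% | 5.7% | 43.7% | 37.9 | yes |
| 5/20 | 25% | 8.7% | 49.1% | 40.4 | yes |
| 6/20 | 30% | 11.9% | 54.3% | 42.4 | yes |

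The printed interval is the row for 4/20. That is also the smallest count whose lower limit exceeds 5%, which is a natural reason for a design to quote it. Over every n from 5 to 100 and every count, 4/20 is the only case whose exact 95% limits round to (6%, 44%).

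**Step 4: look for another method that would give (6%, 44%) at 30%.** Other 95% intervals for 6/20:

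- Wald (9.9%, 50.1%)
- Wilson (14.6%, 51.9%)
- Agresti-Coull (14.3%, 52.1%)
- Jeffreys (13.6%, 51.7%)
- mid-P (13.2%, 52.3%)

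Clopper-Pearson at 90% confidence gives (14.0%, 50.8%). None matches.

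Across all counts from 0 to 20 at n = 20, and across Clopper-Pearson, Wald, Wilson, Agresti-Coull and Jeffreys, only two intervals round to (6%, 44%). One is Clopper-Pearson for 4/20. The other is Wald for 5/20: 0.25 ± 1.96 × √(0.25 × 0.75 / 20) = 0.25 ± 0.190, or (6.0%, 44.0%). The Wald reading requires both the stated rate and the named method to be wrong, and Step 1 shows the named method was applied correctly to Cohort 2. It is possible but less likely.

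**The case against.** The strongest objection is that the figure no longer does any work. Protocol 9.3 makes safety and tolerability the endpoint. Protocol 9.3.2 says efficacy data are no longer collected. SAP 2.3 already presents the calculation as a past rationale. The planned safety analyses are descriptive and do not refer to this interval. Amendment 7 completes enrolment, so a corrected interval would not change recruitment. The slip also does not flatter the design on its own criterion: if 30% was meant, the true lower limit of 12% clears 5% by more than the printed 6%. On this view, the live problem in Protocol 9.3.1 is its present-tense efficacy design, which conflicts with the sections around it. It can also be said that 25% deserves little weight as a correction, because neither document mentions that rate.

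Most of this stands, and it limits the weight of the point. It does not remove the error. The statement is in the current text of both documents, outside any amendment log, and it is the only stated basis for a cohort size that both still give. If 30% was meant, the printed width of 38 points understates the true width of 42. The present-tense wording does need correcting, and that fits in the same edit. The 25% reading is the least likely of the three, but only the sponsor can exclude it.

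**Conclusion.** The concern holds. At n=20 and an observed 30%, the exact Clopper-Pearson 95% interval is (12%, 54%), not (6%, 44%). This is one slip, carried in both Protocol 9.3.1 and SAP 2.3. If 30% was intended, the limits are about 6 and 10 points too low. If 20% was intended, the interval is right and the rate is 10 points too high. If 25% was intended, both the rate and the interval need correcting.

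The arithmetic rests only on inputs that the documents state. Which element is wrong cannot be settled from them; the 20% reading fits the named method and the 5% criterion best. The consequence is limited to the stated precision for Cohort 1. The lower limit exceeds 5% at 4/20, 5/20 and 6/20, so the choice of n=20 is not undermined, and no planned safety analysis changes.

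**What to change.** Confirm the response rate intended for Cohort 1 and print the matching exact interval in both Protocol 9.3.1 and SAP 2.3:

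- 20% (4/20): (6%, 44%)
- 30% (6/20): (12%, 54%)
- 25% (5/20): (9%, 49%), only if the sponsor's records show that this rate was meant

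In the same edit, mark Protocol 9.3.1 as the original design rationale superseded by Amendment 7, as SAP 2.3 already does. The correction costs one line in each document and changes neither enrolment nor any planned safety analysis.

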## 9.3.2 Data Handling Rules for Efficacy Endpoint Analyses

With Amendment 7, efficacy assessments will no longer be collected, and the primary objective is the evaluation of safety and tolerability of miransertib. Therefore, data handling rules for efficacy endpoint analyses are no longer applicable with the adoption of Amendment 7.

#### 9.4 Safety Analysis

All participants who receive at least one dose of study treatment will be evaluated for safety. The incidence rates of TEAEs, treatment-related adverse events, and serious adverse events (SAEs will be described, as identified with preferred terms and MedDRA system organ class.

The frequency of occurrence of overall toxicity, categorized by the maximum toxicity grades (severity), will also be described. Listings of laboratory test results and CTCAE grades will be generated, and descriptive statistics summarizing the changes in laboratory tests over time will be presented.

The safety analyses will be presented by dose and overall using the Safety Population. Safety assessments include AEs, 12-lead ECGs, physical examination, clinical laboratory, and home fasting glucose measurements.

Adverse events will be graded according to the current version of CTCAE.

Exploratory analyses will also be performed on other safety parameters, as deemed appropriate, and within subgroups defined by age, sex, race, mutation status, prior therapies, medical history, and other prognostic factors. Exploratory analyses may also be performed on previously collected laboratory analytes, including PK samples.

Exposure to study treatment over time will be summarized with time on treatment, total amount of administered treatment, dose intensity and relative dose intensity.

## 9.5 Pharmacokinetic Analysis

Summary statistics for steady-state trough (predose) levels may be computed from previously collected samples. PK data may be used in an exposure-response analysis for safety and efficacy. Details will be provided in the SAP.

## 9.6 Data Monitoring Committee

The DMC will monitor patients' safety by reviewing and evaluating study data, reviewing study conduct and progress, and making recommendations concerning the continuation, modification, or termination of the study. DMC meetings will take place at least 2 times per year. There will be a formal charter outlining DMC membership and responsibilities.

# 10 COMPLIANCE WITH GOOD CLINICAL PRACTICE AND ETHICAL CONSIDERATIONS

## 10.1 Institutional Review Board or Independent Ethics Committee Approval

The protocol, any protocol modifications, the ICF, and, if applicable, permission to use private health information must be approved by the investigator's IRB/IEC before study initiation. Documentation of this approval must be provided to the Sponsor or designee and made available during an inspection by the FDA or other regulatory agency inspectors. The investigator will also provide the Sponsor with the General Assurance Number documenting that the IRB/IEC is duly constituted, as well as a list of the names, occupations, and affiliations of the members of the IRB/IEC when available.

Before initiating a study, the investigator/Institution should have written and dated approval/favorable opinion from the IRB/IEC and where applicable, competent authorities/regulatory bodies for the protocol/amendment(s), written ICF, participant

recruitment procedures (eg, advertisements), and written information to be provided to participants.

#### 10.2 Compliance With Good Clinical Practice and Ethical Considerations

This study must be conducted in compliance with IRB/IEC informed consent regulation and the ICH GCP guidelines. In addition, all local regulatory requirements will be adhered to, in particular those affording greater protection to the safety of the study participants.

This study will also be conducted according to the current revision and all subsequent revisions of the WMA Declaration of Helsinki – Ethical Principles for Medical Research Involving Human Subjects and with local laws and regulations relevant to the use of new therapeutic agents in the country of conduct.

Changes to the protocol will require written IRB/IEC and, where applicable, competent authorities/regulatory bodies approval/favorable opinion before implementation, except when the modification is needed to eliminate an immediate hazard(s) to participants.

## 10.3 Participant Information and Consent/Assent

The investigator, or designee, is responsible for the content of the ICF and Assent Form, but the original and any updated versions must be approved by the Sponsor before submission to the IRB/IEC. The ICF and Assent Form should also include any additional information required by local laws relating to institutional review.

Before the start of any study-related procedures are undertaken, the investigator or designee must obtain written, informed consent and/or assent from each study participant (or his/her legal guardian) in accordance with the ICH document "Guidance for Industry – E6 Good Clinical Practice: Consolidated Guidance" and country specific regulations (eg, 21 CFR Part 50). Informed consent/assent will be obtained by discussing with the participant and his/her legal guardian the purpose of the study, the risks and benefits, the study procedures, and any other information relevant to the participant.

The investigator or designee must explain to the participant and his/her legal guardian that for purposes of evaluating the study results, the participant's private health information obtained during the study may be shared with the study Sponsor, regulatory agencies, and IRBs/IECs, before enrolling that participant into the study. It is the investigator's (or designee's) responsibility to obtain permission to use private health information per HIPAA or GDPR and/or other applicable laws from each participant or, if appropriate, the participant's legal guardian.

The participant or his/her legal guardian will document his/her informed consent/assent by signing the current version of the written, IRB/IEC-approved ICF and/or Assent Form. The person who conducted the informed consent/assent discussion with the participant and/or participant's legal guardian must also sign the ICF and Assent Form. The participant or his/her legal guardian is given a fully executed copy of the ICF and/or Assent Form bearing all appropriate signatures; the original(s) must be maintained in the clinical master files at the site.

All active participants participating on the protocol must be reconsented each time the ICF/Assent Form is updated and re-approved by the IRB/IEC.

#### 11 STUDY MANAGEMENT AND MATERIALS

## 11.1 Monitoring, Verification of Data, Audit, and Inspection

A Sponsor monitor or designee will periodically visit each clinical study site to discuss the progress of the clinical study and to review eCRFs and source documents for accuracy of data recording, study medication accountability, and correspondence. When requested, the investigator must be available to the study monitor for personal, one-to-one consultation.

Periodically, some or all of the facilities used in the study may be reviewed or inspected by the IRB/IEC and/or regulatory authorities. An audit or inspection may include, for example, a review of all source documents, drug records, and original clinical medical notes.

The investigator is to ensure that the study participants are aware of and consent to the review of personal information during the data verification process, as part of the monitoring/auditing process conducted by properly authorized agents of the Sponsor or be subject to inspection by regulatory authorities. In addition, participation and personal information is treated as strictly confidential to the extent of applicable law and is not publicly available.

## 11.2 Data Recording and Retention of Study Data

In compliance with GCP, the medical records/medical notes, and other study-related materials should be clearly marked and permit easy identification of participation by an individual in a specified clinical study.

The investigator is to record all data with respect to protocol procedures, drug administration, laboratory data, safety, and efficacy on the eCRFs.

If the investigator relocates or retires, or otherwise withdraws his/her responsibility for maintenance and retention of the master clinical study records, the Sponsor must be notified in writing so that adequate provision can be made concerning the study documents.

Study documents should be retained for at least 2 years after the approval of a marketing application in an ICH region and until there are no pending or planned marketing applications in an ICH region, or until at least 2 years have elapsed since the formal discontinuation of clinical development of miransertib by the Sponsor. The documents should be retained for a longer period, however, if required by the applicable regulatory requirements or by an agreement with the Sponsor that it will inform the investigator, in writing, as to when the retention of these documents is no longer necessary.

#### 11.3 Electronic Case Report Forms

An EDC system will be used to collect the data in this study. The EDC system provides functionality for the clinical sites to enter the data directly into the eCRFs and respond to data discrepancies. Once the data are entered, the information is encrypted and transmitted over the Internet to a clinical study server where it is electronically reviewed. Any resulting data queries are immediately sent back to the site for resolution. The system automatically keeps a full audit trail of all data changes that occur. The clinical team will undertake additional manual review of the data, but all resulting data queries or clarifications will be entered into the EDC system for resolution. All eCRFs will be completed according to instructions provided in the eCRF Completion Guidelines and ICH/GCP guidelines.

## 11.4 Confidentiality, Publication, and Disclosure Policy

The investigator understands that the Sponsor will use the information developed in the clinical study in connection with the development of miransertib. This information may be disclosed to other clinical Investigators, the FDA, and other government agencies, including publication on public websites, such as www.clinicaltrials.gov.

All information disclosed to the investigator by the Sponsor for the purpose of having the investigator conduct the clinical study described in this protocol, or information generated by the investigator as results in the clinical study shall be treated by the investigator as strictly confidential. The investigator shall not use such information other than for the purpose of conducting the clinical study and may not disclose such information to others, except when such disclosure is made to colleagues and/or employees who reasonably require the information to assist in carrying out the clinical study and who are bound by like-obligations of confidentiality. Notwithstanding, the investigator may use or disclose to others any information which: (i) was known to the investigator before the date of its disclosure; (ii) is now, or becomes in the future, publicly available; or (iii) is lawfully disclosed to the investigator on a nonconfidential basis by a third party who is not obligated to the Sponsor or any other party to retain such information in confidence.

The Sponsor acknowledges that the investigator has certain professional responsibilities to report to the scientific community on findings made in the clinical investigations they conduct. The investigator shall have the right to publish the results of research performed under this protocol, provided that such publication does not disclose any Confidential Information or trade secrets of the Sponsor (other than the data). If the study is conducted as part of a multicenter protocol, the investigator agrees not to independently publish the findings except as part of an overall multicenter publication, unless specifically approved in writing by the Sponsor or unless more than 12 months have elapsed since the last participant in the study has completed his/her study designed treatment.

